intervention include the eCPP costs (e.g., tablet, tech support, and maintenance costs), modification of the EHR, orientation for clinicians, and time for the clinician to introduce the study to parents during well-child visits. Participant costs are primarily the parents' opportunity costs, representing the value of their time spent in the intervention or control condition, respectively. Participant costs include time spent completing the eCPP. Resources used will be translated into costs by multiplying the number of units with the cost per unit for each cost category.

Aim 3: RE-AIM data collection. Process tracking forms will be created to record the evaluation data, if not already part of the RCT outcome data (Table 5). These data will be collected monthly by study staff at each site during the recruitment phase from the 4 primary care practice sites, clinicians, and participants.

Table 5. Data and Source for RE-AIM Evaluation

RE-AIM component	Data and Source
REACH: Proportion and characteristics of parents from the practices that were introduced to and enrolled in the study.	# of monthly well-child visits for children aged 2-5 over course of study recruitment (source: EHR) # of parents who were introduced to the study during a well-child visit (source: EHR) # of parents who enrolled in the study (consented/randomized) # of parents who were not introduced to the study and reason (source: EHR) Characteristics of parents enrolled in the study (source: demographics [C.5.a], Technology Inventory ^a)
EFFICACY: Evaluation of intervention efficacy.	Efficacy of the eCPP intervention is assessed as part of the RCT arm of the study by changes in parenting and child behavior. [Specific Aim 1- RCT (Hypothesis 1a)]
ADOPTION: Characteristics of clinicians and practices oriented and agreeing to deliver the intervention (e.g., introduce the study to eligible parents).	Clinician characteristics: MD or NP, specialty, years in practice, and current practices of managing parenting and child behavior concerns (source: Primary Clinician Survey ^b). Site characteristics: # of patients aged 2-5, average time of well-child visits (source: EHR). # of orientation sessions per practice site and proportion of clinicians that attend the orientation (source: attendance records).

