IMPLEMENTATION: Assessment of the delivery of the introduction of the study by clinicians and associated costs.	Proportion of clinicians that introduce the study to parents of patients aged 2-5 at well-child visits (source: EHR). Tracking and monitoring any implementation adaptations by the clinicians (source: clinicians). NOTE: Evaluation of implementation-related cost will occur as part of data collection and analysis of Aim 2 [Specific Aim 2- cost-effectiveness analysis] .
MAINTENANCE: Evaluation of the practice site maintenance of implementation procedures and participant level maintenance of behavior change.	Evaluation of maintenance of procedures across the study period at the practice sites (source: recruitment rates, # of parents introduced to the study monthly). # of follow-up orientation sessions for clinicians. Assessment of implementation challenges and facilitators, and sustainability of activities in clinical practice (source: post-implementation interviews with clinicians). Maintenance of behavior change over time will be assessed as part of the RCT arm of the study. [Specific Aim 1- RCT (Hypothesis 1b)]

EHR = Electronic Health Record. ^aThe Technology Inventory includes 18 items for parents to respond to about their use and ownership of technology. ^bThe Primary Clinician Survey⁸⁶ is a 25-item measure developed by Metzler and colleagues for their 2014 NIH-funded grant “Parenting Help Online Study” to assess pediatric primary care clinicians’ current practices in helping parents with child behavior problems and parenting concerns. The measure will be used with permission by the authors; no reliability data has been reported. (Appendix B)

Analytic plan.

Aim 1. Test the direct effects of the 6-module eCPP on parenting outcomes (parenting behavior, self-efficacy, and stress) and child outcomes (child problem and prosocial behavior) compared to an enhanced usual care control condition among low-income parents with young children seen in primary care. **HYPOTHESIS 1A:** Relative to parents in the control condition, parents in the eCPP condition will report greater improvements in parenting and child outcomes at the 3-month assessment. **HYPOTHESIS 1B:** The improvements in parenting outcomes and child outcomes the eCPP condition relative to the control condition will be maintained through the 6- and 12-month assessments.

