To determine the effectiveness of the implementation strategy and inform dissemination of the eCPP, a cascaded probability model will be constructed.^{97,98} This will be developed based on the following proportions: (a) the likelihood of clinician adoption at the site [*proportion 1 (pr 1)*], (b) the likelihood of implementation (study introduction) by clinicians at the site [*pr 2*], (c) the likelihood of parent enrollment in the study [*pr 3*], and (d) the likelihood of maintenance of behavior change by the eCPP participants [*pr 4*]. *Pr 4* is defined as the proportion of participants whose parenting and child behavior outcomes are the same or improved at the 12-month data collection compared to the 6-month data collection. The estimated likelihood of parents being introduced to the program will be the product of *pr1* and *pr2*. Second, the compound likelihood of parent enrollment in the study will be the product of *pr1*, *pr2*, and *pr3*. Finally, we will estimate the compound likelihood of maintaining behavior change by examining the product of *pr1*, *pr2*, *pr3*, and *pr4*. This analysis will provide us with two important pieces of information: (1) the probable benefits of the program in terms of how likely it is for parents to achieve maintenance of behavior change and (2) inform us of the phase of the implementation process (as operationalized by *pr1*, *pr2*, *pr3*, and *pr4*) which is likely to interfere with the dissemination of the eCPP.

We will conduct a content analysis of the post-implementation interviews with the clinicians. We will use a coding-based system of content obtained from the interviews using the notes taken during the interview using Atlas.ti software. Atlas.ti allows for the identification, organization, and systematizing of codes that can then be assessed in the context of the clinician interviews. Themes will be summarized by site and used to inform the development of processes and procedures to support the implementation and dissemination of the eCPP in pediatric primary care practice sites.

Bibliography & References Cited

1. Children's Defense Fund. Child poverty in America 2013: State analysis. <http://www.childrensdefense.org/zzz-child-research-data-publications/data/child-poverty-in-america-1.pdf>. Updated 2014. Accessed January 12, 2015.

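### Does the Aim 3 cascade misstate the likelihood that a parent is introduced to the program, because pr1, pr2 and pr3 have no stated denominators?

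*Combined protocol and SAP*

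**What the plan says.** The cascade is in the Analytic plan under Aim 3. pr1 is the likelihood of clinician adoption at the site, pr2 is "the likelihood of implementation (study introduction) by clinicians at the site" and pr3 is "the likelihood of parent enrollment in the study". Only pr4 is defined over a stated group: participants whose outcomes at 12 months are no worse than at 6 months. Then "The estimated likelihood of parents being introduced to the program will be the product of" pr1 and pr2. Multiplying in pr3 gives the compound likelihood of enrollment, and multiplying in pr4 gives that of maintained change. The factors are also meant to show which phase of implementation may hold back dissemination.

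Table 5 lists what is collected:

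- **Adoption**, described as "Characteristics of clinicians and practices oriented and agreeing to deliver the intervention", includes the "proportion of clinicians that attend the orientation".
- **Implementation** includes the "Proportion of clinicians that introduce the study to parents of patients aged 2-5 at well-child visits (source: EHR").
- **Reach** is described as the share and profile of the practices' parents who were introduced and who enrolled. It lists the number "of monthly well-child visits for children aged 2-5 over course of study recruitment (source: EHR"), the number "of parents who were introduced to the study during a well-child visit (source: EHR"), the number enrolled, and the number not introduced, with the reason.

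The Aim 3 analysis also promises descriptive statistics at each RE-AIM level for each site.

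**The concern.** pr1 and pr2 carry the RE-AIM names Adoption and Implementation, and the proportions listed under those names in Table 5 have clinicians as their unit. An analyst who simply matched labels would multiply two shares of clinicians and report the result as a likelihood for parents. A clinician who introduced the study to one family would count the same as one who introduced it to every family, because Table 5 sets no minimum. The share of eligible parents whom each clinician approaches would appear in none of the four factors.

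Two things would be at stake. The reported likelihood of introduction, and the products built on it, could be wrong. The cascade could also name enrollment as the weak step when introduction is weaker.

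**Working it through.** The plan states no value for any factor or product, so there is no figure to reproduce. All numerical inputs below are assumptions for illustration.

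**1. Clinician-level reading.** Let a be the share of clinicians adopting, c the share of adopters who introduce the study at all, and v the mean share of eligible parents whom those clinicians approach. Assume equal patient loads and introductions by adopters only. The true share of parents introduced is a × c × v.

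- pr2 among adopters: product = a × c, so product/true = 1/v.
- pr2 over all clinicians: product = a × (a × c), so product/true = a/v.

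Take 10 clinicians, 8 attending orientation and 6 of those 8 introducing: a = 0.80, c = 6/8 = 0.75. The products are 0.80 × 0.75 = 0.60 and 0.80 × 0.60 = 0.48.

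| v | True share (0.60 × v) | 0.60 / true | 0.48 / true |
|---|---|---|---|
| 1.0 | 0.60 | 1.00 | 0.80 |
| 0.8 | 0.48 | 1.25 | 1.00 |
| 0.5 | 0.30 | 2.00 | 1.60 |
| 0.3 | 0.18 | 3.33 | 2.67 |

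Relaxing the assumptions moves the answer again. If the six introducers see 80% of parents and approach 90% of them, the true share is 0.80 × 0.90 = 0.72, against a product of 0.60 with pr2 among adopters.

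**2. Misplaced bottleneck.** On the same reading, with pr2 among adopters and pr3 = enrolled/introduced = 0.40, the factors are 0.80, 0.75 and 0.40 and point to enrollment. Introduction is in fact the weaker step when c × v < 0.40, that is v < 0.40/0.75 = 0.53. The threshold is 0.20/0.75 = 0.27 if pr3 = 0.20, and 0.60/0.75 = 0.80 if pr3 = 0.60.

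**3. Sequential reading, counted in parents.** Let pr1 be the share of eligible parents seen by adopting clinicians, pr2 the share of those who are introduced, and pr3 enrolled/introduced. If only adopters introduce, pr1 × pr2 = introduced/eligible and pr1 × pr2 × pr3 = enrolled/eligible. In the example with v = 0.3 this gives 0.18, the true value.

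If the two non-attenders also introduce and all eight introducers approach 90%, the true share is 0.80 × 0.90 = 0.72. A pr2 limited to adopters' parents is 6 × 0.90/8 = 0.675, and the product is 0.80 × 0.675 = 0.54, which is short. The direct ratio introduced/(introduced + not introduced) is 0.72 in that case too, provided the two counts together cover the eligible parents.

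**4. Which reading the documents support.** The cascade text does not point to the Table 5 clinician proportions. It calls the model cascaded and its products compound, which implies that each factor is conditional on the one before. That makes two branches strained:

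- Taking pr2 over all clinicians would count adoption twice.
- Taking pr3 as enrolled/eligible would make pr3 already the quantity that the three-term product is said to estimate.

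The Reach row, by contrast, is about parents introduced and enrolled, and its counts give introduced/(introduced + not introduced) and enrolled/introduced with no new data.

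**The case for a change.** The strongest case for a change is that label matching is a natural way to read the plan. pr1 and pr2 are described by reference to clinicians, and Table 5 offers a ready-made clinician proportion for each. Two analysts with the same data could therefore report different introduction likelihoods and name different weak steps, and a few lines of text would prevent it. The sequential reading in parents also needs eligible children and introductions tabulated by clinician, which Table 5 does not list.

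Some of this stands. The definitions are missing, the algebra in steps 1 and 2 is right on its assumptions, and clinician shares would be the wrong inputs. But the harm requires an analyst to choose inputs that the plan does not prescribe, for a quantity labeled as a parent likelihood, with parent counts in the same table. The lack of a clinician-level tabulation does not block the result, since the direct Reach ratio gives the introduction likelihood without it. A low introduction rate would also show regardless of how the cascade was built: parents not introduced are counted with reasons, introductions are tracked monthly under Maintenance, and results are described by site.

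**Conclusion.** The concern does not call for a change. The plan leaves pr1, pr2 and pr3 without written denominators, but the default reading is sensible: each step conditional on the last, with introduction and enrollment taken from the Reach counts. Read that way, the introduction and enrollment products are what the plan says they are.

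The size of any error under the clinician-level reading cannot be fixed from the documents. With pr2 among adopters, equal loads and only adopters introducing, it is 1/v, which runs from none at v = 1 to 3.3-fold at v = 0.3, and every value of v is assumed. Understatement arises only by adding a strained denominator or by relaxing those load and adopter assumptions.

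The effect is confined to descriptive products serving a research question with no hypothesis test. The randomized comparison in Aim 1 and the cost-effectiveness analysis in Aim 2 do not use them. The conclusion assumes that the introduced and not-introduced counts are kept per parent and together cover the eligible families. The visit count in the Reach row would be a poorer denominator, since a child may have more than one well-child visit.
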